---

**STATISTICAL ANALYSIS PLAN**

---

**STATISTICAL ANALYSIS PLAN**

---

## STATISTICAL ANALYSIS PLAN

---

### 1. Analysis Considerations

#### 1.1 General Analysis Approach

The main analysis strategy for the primary outcome will be the intention-to-treat (ITT) principle. In this analysis, patients will be analysed according to the arm of randomisation, irrespective of the treatment that was actually given. These ITT analyses will be followed by the per protocol (PP) analysis. In this analysis, only those that adhered to the protocol with respect to the primary outcome will be included for analysis of the primary outcome. All participants will be included in the Intention to Treat (ITT) analysis to maintain the balance achieved through randomisation. For the Per Protocol Analysis (PPA), patients who meet exclusion criteria before hospital discharge or who receive an alternative non-infectious diagnosis during the trial will be excluded.

Key secondary endpoints such as Days of Therapy (DOT), safety and tolerability data will be analysed similar to the ITT approach for the main primary outcome. In this analysis, patients will be analysed according to the arm of randomisation irrespective of the treatment that was actually given, and all patients will be included in the analyses irrespective of their follow-up status, provided data collection is complete. Withdrawals and losses to follow up will not affect the analyses of this data as long as the relevant data needed for these analyses is available prior to withdrawal or loss to follow up.

Data analysis will be performed using Stata 18 or higher, StataCorp, [name] or in R software.

#### 1.2 Data cleaning and verification

All data will be cleaned and verified prior to statistical analysis. The study site is visited by the Study Monitor periodically at time points agreed on with the Investigators. At the time of each monitoring visit, the Study Monitor will review the completed CRFs to ascertain that all items have been completed and that the data provided are accurate and obtained in the manner specified in the protocol. The Study Monitor will also check that the data in the CRF are consistent with the clinical records (Source Data Verification [SDV]) and that study results are recorded completely and correctly. The Data Manager will ensure that clean data is submitted to the statistician for analysis. The statistician will cross-check that the available data for analysis is clean. Any data cleaning queries will need to be resolved before statistical analyses.

#### 1.3 Locking the dataset

After data cleaning and responding to all data queries, the clean data will be locked in the database that was used for data capturing. The data may also be locked and stored in other user-friendly formats such as MS Excel and Stata. The locked data will be stored at an identifiable secure place and should be available to the relevant researchers upon request following proper request procedures.

#### 1.4 Data format and Analysis logs

Prior to dispensing data to the Trial Statistician, the head of Data Management will make sure that the data to be sent to the Trial Statistician is clean. This will help the statistician to provide the analysis results in a timely manner as there will be a reduced number of queries if clean data is provided. Data will be given to the Trial Statistician by the head of Data Management (or designated person) in a format that is compatible with statistical software reading. Statistical analyses will be performed in Stata, version 18 or higher or R software. Statistical programs and output logs will be kept for all analysis and made available upon request.

---

## STATISTICAL ANALYSIS PLAN

---

### 1.5 Interim analyses

Two interim analyses on clinical /laboratory data are conducted to assess the safety of procalcitonin guided de-escalation of antibiotic therapy. The interim reports will be reviewed by the DSMB. The interim analyses are performed after the first 40 patients, first 250 patients and at additional time-points before the planned interim analyses, as indicated by the DSMB after their review, if deemed necessary. After this, safety analysis will be performed based on recommendations by the DSMB. No stopping rules, either statistical or clinical will be specified. The need to stop the trial will be based on the evaluation of the accumulating data by the DSMB. DSMB evaluation mainly focuses on patient safety data, but efficacy data will also be considered.

The trial Statistician in collaboration with Trial Coordinator produces the report for the DSMB. Only relevant data included in a specific interim report are made available to the DSMB members at the time of sending the report. During a DSMB meeting, the report is presented to the DSMB members by the Trial Coordinator in line with the meeting agenda. In preparation of the scheduled DSMB meetings, the interim report is sent out to the members at least a week before the meeting.

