### Randomisation and blinding

Consecutive patients with suspected sepsis admitted at CMCH are eligible for enrolment, provided informed consent is obtained. After eligibility is confirmed, the patient is randomised to either the experimental (procalcitonin) arm or control (standard therapy) arm. Randomisation and treatment allocation is determined by a central computerized binary sequence number generator in a 1:1 ratio with pre-determined block sizes by the study statistician. The study statistician designs the randomisation schedule. The subject's randomisation number is on the sealed opaque envelope as well as on and insert inside the envelope. The trial staff opens the envelopes sequentially for enrolled trial participants and allocates the patient to the treatment arm that is denoted on the insert of that envelope. The allocated arm is noted on the eCRF and other applicable documents. The medical staff and patients are not blinded to intervention randomisation.

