### 2.3 Determination of sample size

The sample size calculation is based on the expected difference in mean length of antibiotic treatment between the experimental and control arm. Based on retrospectively collected data from CMCH, the mean length of therapy (LOT) in sepsis patients was 5.2 days with a standard deviation (SD) of 8 days. The SD of the duration of antibiotic prescription in population level was derived by dividing the difference between the maximum and minimum value of LOT that was obtained from the retrospective data by four as one of the rules of thumb. The SD is assumed to be the same in the experimental and the control arms. We hypothesize to have a higher mean number of days of LOT in the control group as compared to the experimental group – i.e 5.2 days in the control group vs. 3.2 days in the experimental group, for an absolute reduction of mean LOT of 2 days. The level of significance was set at 5% (i.e., alpha=0.05). Based on these assumptions and estimating with 80% power, a total of 506 participants are required (i.e., 253 in the experimental arm and 253 in the control arm) to verify the study hypothesis. We anticipate a 5% loss to follow-up and to compensate for this, a total of 532 participants will be enrolled (266 in the experimental arm and 266 in the control arm). The sample size calculations have been performed in R software (version 4.2.1).

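### SAP section 1.5 lets efficacy data enter the decision to stop but sets no statistical boundary, so stopping early to claim benefit on length of therapy would not be protected at the 5% level

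*SAP*

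**What the plan says.** SAP section 1.5 describes two interim analyses, after 40 and after 250 patients, whose declared purpose is to assess safety. It allows further time-points before the planned ones if the DSMB asks for them, without a limit on their number. After the planned interims it provides only for safety analyses on the DSMB's recommendation.

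On stopping, the section says "No stopping rules, either statistical or clinical will be specified". The need to stop rests on the DSMB's evaluation of the accumulating data. On what the DSMB looks at, it says "DSMB evaluation mainly focuses on patient safety data, but efficacy data will also be considered".

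Section 2.3 sets alpha at 5% and sizes the trial once: "Based on these assumptions and estimating with 80% power, a total of 506 participants are required". Apart from the resistance comparisons in section 3.6.1, this is the only significance level in the SAP. The document has no alpha-spending function, no adjusted final level, and no statement that the trial will not be stopped for benefit.

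**The concern.** Section 1.5 puts three things side by side: efficacy data are before the DSMB, the decision to stop rests on accumulating data, and no statistical rule applies. The section does not leave the matter to another document; it states that no rule will be set. Taken together, this leaves stopping early because LOT already looks shorter in the procalcitonin arm open and ungoverned.

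If that happened, the final comparison would no longer be a single test at 5%. A 95% confidence interval computed in the usual way would not have its stated coverage, and the estimated reduction would tend to be too large, because the trial would have stopped at a favourable moment. Fewer patients would also contribute to mortality and recurrent infection, the secondary safety endpoints in section 2.1.3 on which a claim of safe reduction depends.

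**Working it through.** **1. Is the stated sample size a fixed-sample figure?**

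Inputs from section 2.3: "5.2 days in the control group vs. 3.2 days in the experimental group, for an absolute reduction of mean LOT of 2 days"; SD 8 days in both arms; alpha 0.05; power 80%. Allocation is 1:1 (section 2.2).

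- Normal approximation: n per arm = 2 × (1.960 + 0.842)² × 8² / 2² = 251.2, so 252.
- Two-sample t-test: 252.13, so 253 per arm and 506 in total. This matches the SAP.
- A one-sided test would give 198 per arm, so the calculation is two-sided, although the SAP does not say so.
- Loss to follow-up: 506 × 1.05 = 531.3, so 532 as stated. (506 / 0.95 = 532.6 would give 533; the difference is immaterial here.)

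The figure is reproduced with one two-sided test at 0.05 and nothing set aside for interim looks.

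**2. What would unadjusted stopping for benefit do to type I error?**

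The SAP gives no interim threshold, so one has to be assumed. Assumptions: LOT is tested at two-sided P<0.05 at each look, the trial stops at the first crossing, and information is proportional to the number of patients. The z statistics at looks with n₁ < n₂ patients then have correlation √(n₁/n₂). The chance of a first crossing at each look under no effect comes from numerical integration:

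| Looks (patients) | First crossing at each look | Overall error |
|---|---|---|
| 532 only | 0.050 | 5.0% |
| 250, 532 | 0.050 + 0.034 | 8.4% |
| 40, 250, 532 | 0.050 + 0.043 + 0.032 | 12.5% |
| 40, 150, 250, 532 | 0.050 + 0.040 + 0.027 + 0.030 | 14.7% |

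The look at 150 is an assumed example of an extra time-point. It is placed before 250 because section 1.5 allows extra interim time-points only before the planned ones.

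**3. Could LOT cross at 250, and what would the estimate look like?**

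Take the SAP's own assumptions (true difference 2 days, SD 8), 125 per arm, and LOT known for all.

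- Standard error = 8 × √(2/125) = 1.012 days.
- Difference needed for P<0.05 = 1.96 × 1.012 = 1.98 days.
- Chance of crossing in favour of procalcitonin = Φ(2/1.012 − 1.96) = Φ(0.016) = 0.51.
- Mean estimate among those crossings = 2 + 1.012 × 0.399 / 0.507 = 2.8 days, against a true 2 days.

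So, if the planning assumptions hold, a nominally significant LOT result at the second interim is about an even chance.

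**4. What does a strict interim limit do?**

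With P<0.001 at every interim look (Haybittle-Peto) and the final test at 0.05, the overall error is 5.1% for looks at 40, 250 and 532, and 5.2% with the extra look at 150. For the planned looks, a final level of 0.0489 brings it back to 5%.

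**The case against.** The interims are declared to be for safety, the DSMB's focus is mainly safety, and what follows the look at 250 is called safety analysis. Efficacy data may be there only so that harm can be weighed against benefit. Monitoring by DSMB judgement is a legitimate design, and no repeated test of LOT is described anywhere. Stopping for LOT alone at 40 patients, about 20 per arm, is implausible, and that look is what raises 8.4% to 12.5%. LOT runs until 28 days after discharge, so interim LOT may be incomplete for recent patients and information need not be proportional to enrolment.

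Most of this stands, and it limits the point. A reader might infer that the plan tests efficacy repeatedly and that its type I error is already inflated to one of the figures above. The SAP does not support that: the percentages describe an assumed way of acting, not the plan. A reader might also infer that any use of efficacy data in a stopping decision inflates the error. It does not; only stopping early to claim benefit does. Nor should efficacy looks after 250 be added to the illustration, because section 1.5 provides only safety analysis there. Finally, that the LOT comparison will be tested at 0.05 is inferred from section 2.3 and the absence of any adjustment; the SAP does not state a final level.

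What the objection does not remove is the gap itself. Section 1.5 does not say that efficacy is for context only, and it rules out the boundary that would be needed if it is not.

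**Conclusion.** The point holds in a conditional form. Section 1.5 admits efficacy data into an unbounded stopping decision while section 2.3 sizes the trial for one test at 5%. If the trial were stopped early to claim benefit on LOT, the nominal error rate and confidence interval would fail and the estimate would tend to be too large.

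The size of the inflation cannot be derived from the SAP. The range of 8.4% to 14.7% is a hypothetical upper illustration that assumes mechanical stopping at unadjusted two-sided P<0.05 and information proportional to patients. If LOT can never trigger stopping for benefit, there is no inflation and the final test can stay at 0.05. This is a gap worth closing with a sentence, not a fault in safety oversight.

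**What to change.** In section 1.5, confine the absence of stopping rules to safety, and add one of two statements on efficacy.

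- **Preferred:** LOT data go to the DSMB for benefit-risk context only, and the trial will not be stopped for benefit on LOT. The final test stays at two-sided 0.05. This is sufficient alone.
- **Alternative:** stopping for benefit on LOT requires two-sided P<0.001 at any interim look, scheduled or not, with the final test at 0.05. The overall error is then about 5.1–5.2% in the schedules checked. If exactly 5% is wanted, the final level becomes about 0.049 for the planned looks.

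Either way, state the final two-sided level for the LOT comparison, which the SAP now leaves to inference.

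The cost is one or two sentences. Planned enrolment, the timing of the interims and the DSMB's discretion on safety are unchanged. The downside is that early stopping for benefit is ruled out under the first option and becomes rarer under the second.

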## 2. Introduction and study summary

Antimicrobial resistance (AMR) is a global problem, resulting in increased morbidity and mortality from multidrug resistant bacterial infections that are challenging to treat. Low- and middle-income countries (LMICs), like Bangladesh, are disproportionately affected by AMR. Excessive use of antibiotics both inside and outside the hospital is thought to be an important driver of AMR in Bangladesh and other LMICs. Several studies have shown that sequential assessment of serum procalcitonin (PCT) concentrations is an effective and safe strategy to shorten the duration of antibiotic therapy in critically ill patients. In this strategy, a decrease of procalcitonin below a certain threshold prompts the clinician to stop or reduce antibiotic treatment. However, these studies were conducted in high resource settings with standard laboratory PCT testing at considerable costs. We propose to evaluate the use of sequential serum PCT measurement to guide de-escalation of antibiotic therapy in a randomised clinical trial in patients with sepsis in a large tertiary referral hospital in Chattogram, Bangladesh, using low-cost point-of-care quantitative procalcitonin measurements. Main endpoint of the trial will be the difference in antibiotic therapy duration between the study groups. If this study shows that PCT guided de-escalation of antibiotics results in a safe reduction in antibiotic usage, this will be an important strategy to reduce the antibiotic burden in hospitals in Bangladesh and comparable resource-limited settings, as well as other consequences of prolonged antibiotic therapy, including increased costs, prolonged duration of intravenous lines and duration of stay, and microbiota changes.

### 2.1 Study objectives and endpoints

#### 2.1.1 Primary objective

To assess the **efficacy** of antibiotic de-escalation rules based on daily procalcitonin measurements to reduce the length of antibiotic treatment in hospitalized patients with sepsis in a low-resourced setting.

#### 2.1.2 Primary endpoint

**Length of antibiotic treatment:** number of days of antibiotic treatment during the study period (till 28 days after hospital discharge). The primary outcome data for participants with recurrent infections will be censored at the time of recurrent infection diagnosis.

---

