### 2.1.3 Secondary objectives and endpoints

- To assess if procalcitonin guided de-escalation reduces antibiotic **consumption** and days of therapy with antibiotics.

- Consumption of antibiotics expressed as the Defined Daily Dosage (DDD)

*Definition of DDD: The basic definition for a defined daily dose is the assumed average maintenance dose per day for a drug used in its main indication in adults. Antibiotic use using the WHO DDD definition ([https://www.whocc.no/atc\\_ddd\\_index/](https://www.whocc.no/atc_ddd_index/)) will be determined for the most frequently prescribed Drugs in Bangladesh*

- Days of therapy with antibiotics (DOT)

Definition of DOT: One DOT represents the administration of a single antibiotic on a given day regardless of the number of doses administered or dosage strength. If a patient receives more than one antibiotic it will be added on with DOT of the first antibiotic. (Dalton et al. 2015)

- Number of days of parenteral antibiotic during hospitalisation period
- Number of days of antibiotic treatment during the hospitalisation period.

- To assess the safety of procalcitonin guided de-escalation of treatment
  - Overall mortality, mortality-associated with recurrent infection, and non-lethal recurrent infections.
- To assess the effect of procalcitonin guided de-escalation on length of hospital stay
  - Duration of hospital stay (ICU/ general ward)
- To determine the spectrum of antimicrobial resistance among bacteria identified in clinical specimens from Bangladeshi patients hospitalized with sepsis
  - Bacterial isolates from blood cultures will be identified, tested for antibiotic susceptibility. In a subset of antibiotic resistant isolates, genetic correlates of resistance will be assessed (A comprehensive microbiological analysis plan is provided in section 3.6).
- To compare the patient care costs between study arms
  - Direct medical costs of prescribed antibiotics, the PCT assay and hospital stay costs.

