**B. Included in Both ITT and PP**

- a. Patients for whom the non-binding advice to stop antibiotics was not followed:
  - Provided the patient does not meet criteria for an alternative diagnosis
- b. Patients presenting with recurrent infections:
  - If it is a recurrent infection the outcome will be censored at the time of recurrent infection. The amount of antibiotic a patient receives after enrollment in the study, up until the occurrence of a recurrent infection episode, will be included in the analysis
- c. Patients discharged before procalcitonin reached the predefined target value for antibiotic de-escalation
- d. Patients who restarted antibiotics without having a recurrent infection:

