**4.1 Guide to the calculation of the Length of Therapy (LOT), Days of Therapy (DOT) and the Defined Daily Dose (DDD)**
**Length of therapy (LOT) calculation.**

LOT is defined as the number of days of antibiotic treatment during the study period. Length of treatment will be measured from the day of enrolment to completion of the study follow up (28 days after hospital discharge). The primary outcome data for participants with recurrent infections will be censored at the time of recurrent infection diagnosis, i.e. the recurrent date will be used as the stop date in the calculation of LOT. If the recurrent infection occurs after the patient already stopped antibiotics for the initial presenting infection, the actual stop date of the last dose of antibiotics administered for the initial infection will be used in the LOT calculations and not the recurrent infection date.

The stop date for each antibiotic will be when the treating team discontinues it. In special circumstances, such as patients who left the hospital against medical advice or were transferred to another facility, the stop date will be recorded as the date they left or were transferred, as it was not feasible for the study team to track antibiotic data consistently in both arms beyond these points. If a patient developed an alternative diagnosis during the study that required an extended or modified antibiotic regimen, each case was reviewed individually by an investigator panel to determine the maximum antibiotic duration that could be included in the analysis.

**Scenario 1:** As an example, suppose patient A was admitted to the hospital on 02 February 24 at 10:00 AM due to a urinary tract infection. At 4:00 PM the same day, this patient was enrolled into the PROCALBAN study and was discharged from the hospital on 08 February 24 at 10:00 AM. This patient received intravenous ceftriaxone, 1 gram administered every 12 hourly from the date of enrolment and then upon discharge, this patient was prescribed oral cefuroxime, 500mg every 8 hours, for a duration of 7 days i.e. the actual stop date time for this oral cefuroxime will be subsequently recorded in the database by the end of follow-up for this patient. The calculation of LOT (the primary outcome) will proceed as follows:

1. Hospital stay duration during enrolment will be calculated as follows:
  - Enrollment: February 2nd, 4:00 PM
  - Discharge: February 8th, 10:00 AM
  - Hospital stay duration:

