## STATISTICAL ANALYSIS PLAN

ceftriaxone every 12 hours, denoted by "1 dot" for each day. Upon discharge, Patient B was prescribed oral amoxicillin 500mg every 8 hours to be taken at home for 7 days, denoted by "1 DOT " for each day.

Calculation:

1. Hospital stay duration: 4 days
2. Intravenous ceftriaxone therapy: Given every 12 hours for 4 days (total of 2 doses per day, counted as "1 DOT " for each day)
3. Oral amoxicillin therapy: Prescribed for 7 days, taken every 8 hours (total of 3 doses per day, counted as "1 DOT " for each day)
4. Overall Therapy Duration: 4 days (hospital stay) + 7 days (oral antibiotic therapy) = 11 DOTs

The actual DOT for each antibiotic drug that was given will be recorded by the end of the patient's follow-up and will be used for the calculations. The actual date (or date time if available) will be used to calculate the DOT for each antibiotic drug and then these DOTs will be summed up.

In calculating DOT, if an antibiotic is administered every 48 hours, it will not be counted as every alternate day. For example, if a patient receives meropenem every 48 hours over a span of 7 days, it will be counted as 7 DOT, not 4 DOT. This approach considers the overall exposure to the antibiotic.

**Number of days of parenteral antibiotic during hospitalisation period:** will be measured from the day of enrolment to the day of stopping of parenteral antibiotic during hospitalisation period

**Number of days of antibiotic treatment during the hospitalisation period:** Length of treatment will be measured from the days of enrolment to stopping of antibiotic during hospitalisation period.

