### 4.2 Considerations for timepoints in calculating Length of Therapy (LOT), Days of Therapy (DOT), and Defined Daily Dose (DDD)

Length of Therapy (LOT)	Days of Therapy (DOT)	Defined Daily Dose (DDD)
Starting Point: Enrolment date and time.	Starting Point: Enrolment date and time.	Starting Point: Enrolment date and time.
Stopping Point: Actual antibiotic stopping time as recorded by the treating team.	Stopping Point: Antibiotic stopping time as per treating team's decision.	Stopping Point: Antibiotic stopping time as per treating team's decision.
Exceptions:  Recurrent Infections: Censor the LOT during recurrent infection episodes.  Left Against Medical Advice (LAMA): Consider the date the patient left as the stopping point.  Transfer to Another Hospital: Use the transfer date as the stopping point.  Atypical Cases: Determine a reasonable stopping date through team discussion.	Exceptions:  Same as those applied in the LOT calculation, using specific stopping points for recurrent infections, LAMA, transfers, and atypical cases.	Exceptions:  Same as those applied in the LOT and DOT calculation, using specific stopping points for recurrent infections, LAMA, transfers, and atypical cases.

---

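### DOT and DDD stop at recurrent infection, so they measure index-episode consumption only; add a supplementary analysis that counts recurrence re-treatment

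*SAP*

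**What the plan says.** For LOT, the stop at recurrence is stated in section 2.1.2 ("The primary outcome data for participants with recurrent infections will be censored at the time of recurrent infection diagnosis") and again in section 3.3, list B, item b ("If it is a recurrent infection the outcome will be censored at the time of recurrent infection"). That item applies to both the intention-to-treat (ITT) and per-protocol sets, and it also limits the amount of antibiotic counted to what was received before the recurrence. Appendix 4.1 adds that, if antibiotics had already ended before the recurrence, "the actual stop date of the last dose of antibiotics administered for the initial infection will be used in the LOT calculations".

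The timepoint table in Appendix 4.2 extends the rule. The DOT column reads "Same as those applied in the LOT calculation, using specific stopping points for recurrent infections", and the DDD column reads "Same as those applied in the LOT and DOT calculation, using specific stopping points for recurrent infections".

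The objective is wider. Section 2.1.3 asks whether procalcitonin guidance reduces antibiotic consumption and days of therapy, and names DDD and DOT as measures. Section 2 gives the trial's purpose as finding out whether the strategy "results in a safe reduction in antibiotic usage". The basic definitions in Appendix 4.1 also look to everything the patient received: for DOT, "The actual DOT for each antibiotic drug that was given will be recorded by the end of the patient's follow-up", and for DDD, the per-patient sum of the doses of each antibiotic administered.

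**The concern.** A patient who stops antibiotics early, relapses and is treated again has used both courses. Under the SAP only the first course enters LOT, DOT and DDD. For a measure of how long the index course lasted, that is a reasonable choice. For a comparison of consumption between arms it removes part of the quantity of interest.

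The removal need not be balanced. Recurrence arises after randomisation, and the SAP lists it as a safety endpoint because earlier stopping might affect it. If the procalcitonin arm has more re-treatment, the truncated DOT and DDD overstate the net saving; if it has less, they understate it. Table 2 would show unequal recurrence, but only as counts and percentages, which a reader cannot turn into days or doses.

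**Working it through.** **Is re-treatment excluded on every reading?** If recurrence comes during the index course, counting ends at the recurrence date. If it comes after the index course, counting ends at the last dose for the initial infection. The LOT column in Appendix 4.2 speaks of censoring during recurrent episodes, which leaves open whether counting resumes afterwards, but treatment of the recurrence is left out either way.

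**Does another planned measure restore it?**
- In-hospital antibiotic days and parenteral days (Appendix 4.1) state no recurrence cut, so they may capture re-treatment given during the stay, but they end with the hospital stay.
- The antibiotic cost sums (section 3.7.1) state neither a recurrence cut nor a time window. They may capture some re-treatment, but in money.
- Table 2 gives recurrence as n (%) only.

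None of these measures total use to 28 days after discharge.

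**Planning figure (section 2.3).** Inputs: difference 2 days (5.2 v 3.2), SD 8, alpha 0.05 (two-sided assumed), power 80%. The normal approximation, 2 × (1.96 + 0.84)² × 8² / 2², gives 252 per arm. The t-test version gives 252.13, rounded up to 253 per arm, or 506 in total, as stated. The 2-day target and SD are used below as the reference.

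**Size of the shift.** Let r be the recurrence rate and d the mean re-treatment days in each arm. Then

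difference including re-treatment = 2.0 − (r_PCT × d_PCT − r_control × d_control).

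The SAP gives neither r nor d, so all values here are assumptions.

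| r, PCT v control | d, days | Calculation | Difference, days |
|---|---|---|---|
| 5% v 5% | 7 | 2 − (0.35 − 0.35) | 2.00 |
| 10% v 10% | 10 v 7 | 2 − (1.00 − 0.70) | 1.70 |
| 10% v 5% | 7 | 2 − (0.70 − 0.35) | 1.65 |
| 10% v 5% | 10 | 2 − (1.00 − 0.50) | 1.50 |
| 15% v 5% | 10 | 2 − (1.50 − 0.50) | 1.00 |
| 5% v 10% | 7 | 2 − (0.35 − 0.70) | 2.35 |
| 5% v 10% | 10 | 2 − (0.50 − 1.00) | 2.50 |

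To remove the whole 2 days, the procalcitonin arm would need an excess of 2/10 = 20 percentage points at 10 days per course, or 2/7 = 28.6 points at 7 days.

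**Precision.** For truncated LOT, SE = 8 × √(2/253) = 0.711, a 95% half-width of 1.96 × 0.711 = 1.39 days. Including re-treatment, take the variance per arm as 64 + r(1 − r)d², with d fixed and independent of the index course (both assumed). The smallest case (5% v 5%, 7 days) gives √[(66.33 + 66.33)/253] = 0.724. The largest (15% v 5%, 10 days) gives √[(76.75 + 68.75)/253] = 0.758. The half-widths are 1.42 to 1.49 days.

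**Why the LOT formula cannot be reused.** Appendix 4.1 sums LOT up as last stop minus first start. A patient who stops at day 3 and restarts at day 20 for 10 days has a truncated value of 3, a sum of treated days of 13, and a last-stop-minus-first-start value of 30, of which 17 days are antibiotic-free.

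**The case against.** The strongest reply is that the rule is deliberate. It appears in several sections, and list B, item b speaks of the amount of antibiotic rather than LOT alone, so the truncation of DOT and DDD is not a slip in one table. Section 2.1.3 gives DOT and DDD no time window of their own, and Appendix 4.2 supplies one. Recurrence is reported by arm beside the usage metrics. This stands: the SAP chose a narrower quantity and did not contradict itself, and index-episode DDD is still a measure of consumption. What remains is that the narrower quantity does not answer the objective as worded, and nothing planned supplies the wider one.

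It is also fair that the figures above are hypothetical and in antibiotic days. The SAP has no planning values for DOT or DDD, so no shift can be worked out on those scales. Five of the seven scenarios other than the extremes, and the 2.50-day case as well, move the difference by 0.5 day or less, against a half-width of 1.39. Variable re-treatment lengths would widen the interval somewhat beyond 1.49.

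Finally, recurrence is not the only cut. The SAP also stops counting at transfer, leaving against advice, alternative diagnosis, start of prophylaxis and last follow-up, and it leaves out post-discharge restarts for other reasons. Adding back recurrence alone does not give total use. This stands, and the fix has to deal with it.

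**Conclusion.** The point holds for DOT and DDD as measures of the consumption objective. They describe index-episode consumption, and if re-treatment differs by arm they misstate the net saving. With assumed recurrence of 5–15% and 7–10 re-treatment days, a 2.0-day difference would lie between 1.0 and 2.5 days. It is unchanged when the two products r × d are equal.

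A reader might infer three stronger things that the SAP does not support:
- That the primary endpoint is wrong. LOT cut at recurrence is a pre-specified measure of index-course length and is valid for what it defines.
- That the rule favours the procalcitonin arm. The direction depends on recurrence rates and re-treatment lengths that the SAP does not give.
- That the saving could plausibly vanish. That would take a 20- to 29-point excess in recurrence at 10 or 7 days per course.

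The reading of the text is secure; the size rests wholly on the stated assumptions. It should be settled before the analysis.

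**What to change.** Keep the primary LOT unchanged. Label LOT, DOT and DDD as index-episode measures in section 2.1.3, Table 2 and Appendix 4.2. Then add one pre-specified supplementary ITT analysis of antibiotic days, DOT and DDD from enrolment to 28 days after discharge that includes re-treatment of recurrences:

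- Sum treated days across courses, and do not use last stop minus first start.
- State whether each other cut applies: transfer and leaving against advice (Appendix 4.1), alternative diagnosis (Appendix 4.2, atypical cases), prophylaxis and missing 28-day follow-up (section 3.3, list A, items g and f), and post-discharge restarts for other reasons (list B, item d).
- If any cut remains, describe the result as including recurrence treatment and not as total use.
- Report the estimate with its 95% interval, and word any claim of reduced consumption in light of it.

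The cost is SAP wording and some derivation work. Sample size does not change. Appendix 4.1 says the DOT of each antibiotic given is recorded by the end of follow-up, but the sponsor must confirm that this covers dates and doses after a recurrence. The drawback is an effect that may be smaller and slightly less precise.
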